## **6.6 Availability**

Ponatinib will be provided free of charge to study participants by Ariad.

## **6.7 Storage**

Bottles containing ponatinib tablets should be stored at room temperature.

All investigational products should be stored in a secure area according to local regulations. The investigator is responsible for ensuring that it is dispensed only to study participants and only from official study sites.

## **6.8 Ordering**

Each investigative site will order ponatinib directly through Ariad. Shipments will be at appropriate intervals, depending on patient accrual. Each site must use an appropriate dispensing log/accountability form provided by the Sponsor, or an acceptable substitute approved by the Sponsor. Each time study medication is dispensed for a participant, the following information must be recorded: the patient's initials, the patient's study number, tablet strength (45 mg or 15 mg), the number of tablets dispensed with the corresponding lot number, and the initials of the person dispensing the drug. Ponatinib may be repackaged by the site pharmacy and is typically supplied in bottles containing 60 tablets. If repackaged, ponatinib should be placed into a high density polyethylene (HDPE) bottle. These logs are to be maintained by the study pharmacist in the pharmacy throughout the duration of the study. Logs at non-DF/HCC sites will be periodically verified by a representative of the Sponsor. The Investigator is responsible for ensuring that the patient diary card(s) and study drug provided to the participant and returned from the participant are accounted for and noted in source documentation.

## **6.9 Accountability**

The investigator will ensure that a current record of disposition of investigational product is maintained at each study site where the investigational product is inventoried and disposed.

Ponatinib dispensing record/inventory logs and copies of signed packing lists must be maintained at the investigational site. Batch numbers for ponatinib must be recorded in the drug accountability records.

## **6.10 Destruction and Return**

If the investigational product is to be destroyed on site, it is the investigator's responsibility to ensure that arrangements have been made for disposal, and that procedures for proper disposal

have been established according to applicable regulations, guidelines, and institutional procedures. Appropriate records of the disposal must be maintained.

Consult with the Principal Investigator for instructions on disposal of unused ponatinib tablets.

### **6.11 Required Concomitant Therapy**

Ponatinib has been associated with an increased risk for arterial thrombotic events, such as myocardial infarction, peripheral vascular disease and cerebrovascular accident.

Thromboprophylaxis is required for all participants receiving ponatinib. It is recommended that participants receive daily aspirin (81 or 325 mg). Note: This does not apply to participants who are already receiving therapeutic anticoagulation (e.g. low molecular weight heparin), provided that these participants meet the eligibility criteria outlined in [Sections 3.1 and 3.2](#). It is recommended that if the platelet count falls below 50,000/mm^3, thromboprophylaxis be held to minimize the risk of bleeding. It should then be resumed when platelet counts are equal to or above this level.

All patients should also be treated with a statin to reduce the risk of cardiovascular events. We recommend atorvastatin (Lipitor) administered at a minimum of 10 mg/day, but other statins and doses may be substituted if appropriate. The specific regimen should correspond with moderate-intensity or high-intensity statin therapy as defined by the recent AHA/ACC guidelines (Stone et al, Circulation 2013,

<http://circ.ahajournals.org/content/suppl/2013/11/07/01.cir.0000437738.63853.7a.DC1.html>).

High-intensity therapy should be considered in patients in high risk categories, such as those with a history of cardiovascular disease, diabetes, or LDL cholesterol greater than 190 mg/dL, but patient age and risk of side effects due to statin therapy (myopathy, elevated CPK, elevated liver enzymes) should be taken into consideration. Measurement of cholesterol and dose adjustment to meet a cholesterol target is not necessary but could be considered to ensure compliance or per physician or patient preference.

### **6.12 Permitted Treatment**

All routine and appropriate supportive care, including blood products, will be provided during this study, as clinically indicated, and in accordance with the standard of care practices. Please see [Section 7](#) for management of expected adverse events (AEs).

Palliative radiation therapy will be permitted for participants with symptomatic bone metastases or CNS metastases as long as they have demonstrated stability in terms of systemic disease. Disease stability for these purposes will be defined as complete response, partial response, stable disease or clinical benefit in the opinion of the Investigator. For participants undergoing radiation, ponatinib must be held for at least 72 hours before the initiation of radiation. Ponatinib may be resumed no sooner than 72 hours after the completion of radiation.

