### **3.2 Exclusion Criteria**

Patients who exhibit any of the below findings at the time of screening will not be eligible for admission into the study.

- 3.2.1 Major surgery within 28 days prior to initiating therapy.
- 3.2.2 History of CNS disease. Note: Patients with brain metastases will be eligible if treated appropriately and if they remain clinically stable neurologically. For asymptomatic brain metastases, appropriate clinical treatment may include observation with serial imaging.
- 3.2.3 Participants who have received systemic chemotherapy within 3 weeks of starting study drug.
- 3.2.4 Participants who have received treatment with a TKI within 7 days of the first dose of study treatment. An alternative appropriate wash-out period based upon the known half-life of the agent and reversibility of drug-related adverse events may be considered after consultation with the study sponsor.
- 3.2.5 Participants who have received radiation therapy within 2 weeks of starting study drug. Note: Participants who have received radiation therapy to a small volume (e.g. stereotactic radiosurgery to the CNS) will be eligible if completed > 1 week prior to starting study drug.
- 3.2.6 History of significant bleeding disorder unrelated to cancer.
- 3.2.7 History of acute pancreatitis within 1 year of study entry or history of chronic pancreatitis.
- 3.2.8 History of or ongoing alcohol abuse that, in the opinion of the Investigator, would compromise compliance or impart excess risks associated with study participation.
- 3.2.9 Uncontrolled hypertriglyceridemia (triglycerides > 450 mg/dL). If a patient is excluded solely based upon a non-fasting triglyceride level, a fasting test should be performed to determine eligibility.

3.2.10 Study participants must have had prior EGFR and ALK testing. Participants with sensitizing mutations in EGFR or ALK rearrangements will be excluded.

3.2.11 History of arterial thrombotic disease, specifically including, but not restricted to:

- Myocardial infarction or unstable angina.
- Cerebrovascular event (CVA) or transient ischemic attack (TIA).
- Peripheral vascular disease or claudication.

3.2.12 Significant uncontrolled or active cardiovascular disease, specifically including, but not restricted to:

- History of clinically significant (as determined by the treating physician) atrial arrhythmia; or any ventricular arrhythmia.
- History of congenital long QT syndrome.

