#### 9.1.2 Disease Parameters

Measurable disease. Measurable disease is the presence of at least one (1) lesion that can be accurately measured in at least one dimension with longest diameter  $\geq 20$  millimeters (mm) using conventional techniques (x-ray) or  $\geq 10$  mm with spiral CT scan. Measurable lesions must be at least 2 times the slice thickness in mm. All tumor measurements must be recorded in millimeters (or decimal fractions of centimeters).

**Note:** A lesion in a previously irradiated area is not eligible for measurable disease unless there is objective evidence of progression of the lesion prior to study enrollment. Lesions in previously irradiated areas must be clearly identified as such.

Malignant lymph nodes. To be considered pathologically enlarged and measurable, a lymph node must be  $\geq 15$  mm in short axis when assessed by CT scan (CT scan slice

thickness recommended to be no greater than 5 mm). At baseline and in follow-up, only the short axis will be measured and followed.

**Non-measurable disease.** All other lesions (or sites of disease), including small lesions (longest diameter < 10 mm or pathological lymph nodes with  $\geq$  10 to < 15 mm short axis), are considered non-measurable disease. Bone lesions, leptomeningeal disease, ascites, pleural/pericardial effusions, lymphangitis cutis/pulmonis, inflammatory breast disease, abdominal masses identified by physical exam that are not measurable by reproducible imaging techniques, and cystic lesions are all considered non-measurable.

**Target lesions.** All measurable lesions up to a maximum of 2 lesions per organ and 5 lesions in total, representative of all involved organs, should be identified as target lesions and recorded and measured at baseline. Lesions must be accurately measured in 1 dimension with a minimum size of 10 mm by CT or MRI (slice thickness no greater than 5 mm), 20 mm by *chest x-ray*. Nodes must have a short axis  $\geq$  15 mm. The short axis should be included in the sum of the lesions in the calculation of response. Nodes that shrink to < 10 mm are considered normal. Target lesions should be selected on the basis of their size, be representative of all the involved organs, and should be lesions that can be followed with reproducible repeated measurements.

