Lytic bone lesions or mixed lytic-blastic lesions, *with identifiable soft tissue components*, that can be evaluated by cross sectional imaging techniques such as CT or MRI can be considered target lesions if the *soft tissue component* meets the definition of measurability as defined above. Cystic lesions thought to represent cystic metastases can be considered as target lesions. However, if non-cystic lesions are present, these are preferred for selection as target lesions. Lesions in previously irradiated areas or areas subject to other loco-regional therapy are usually not considered measurable unless there has been demonstrated progression of that lesion.

**Non-target lesions.** All other lesions, including small lesions < 10 mm or pathological lymph nodes measuring  $\geq$  10 mm to < 15 mm in short axis, as well as truly non-measurable lesions, which include leptomeningeal disease, ascites, pleural or pericardial effusion, inflammatory breast disease, lymphangitic involvement of skin or lung, abdominal masses identified by physical exam that are not measurable by reproducible imaging techniques.

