### **9.1.3 Response Criteria**

#### ***Evaluation of Target Lesions***

**Complete Response (CR):** Disappearance of all target lesions. Any pathological lymph node must have reduction in short axis to < 10 mm.

**Partial Response (PR):** At least a 30% decrease in the sum of the diameters of target lesions, taking as reference the baseline sum diameters.

**Progressive Disease (PD):** At least a 20% increase in the sum of the diameters of target lesions, taking as reference the smallest sum on study with at least a 5 mm absolute increase in the sum of all lesions. The appearance of one or more new lesions\* denotes disease progression.

Stable Disease (SD): Neither sufficient shrinkage to qualify for PR nor sufficient increase to qualify for PD, taking as reference the smallest sum diameters while on study.

Unknown (UN): Assessment of target lesions cannot be made due to insufficient or unevaluable data. In this case, a concise explanation must be given.

**Note:** If tumor response data is missing for target lesions, the overall assessment must be UN unless there is new disease that would result in an overall assessment of PD. However, if there is missing or unevaluable data for non-target lesions, but data is available for all target lesions, the overall response for that time point will be assigned based on the sum LD of all target lesions. Additionally, the assessment of CR cannot be made if there is missing or unevaluable data for non-target lesions. In this case, the overall assessment would be PR.

**\*Definition of New Lesion:** The finding of a new lesion should be unequivocal (i.e. not due to difference in scanning technique, imaging modality, or findings thought to represent something other than tumor (ex: new bone lesions may be healing or flare of pre-existing lesions)). However, a lesion identified on a follow-up scan in an anatomical location that was not scanned at baseline is considered new and will indicate PD. If a new lesion is equivocal (because of small size, etc.), follow-up evaluation will clarify if it truly represents new disease and if PD is confirmed, progression should be declared using the date of the initial scan on which the lesion was discovered.

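### Section 9 does not say how a target lesion irradiated on study is scored, so radiation shrinkage could count toward the primary response rate

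*Combined protocol and SAP*

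**What the plan says.** **Radiation on study.** Section 6.12 states: "Palliative radiation therapy will be permitted for participants with symptomatic bone metastases or CNS metastases as long as they have demonstrated stability". It then sets the standard: "Disease stability for these purposes will be defined as complete response, partial response, stable disease or clinical benefit in the opinion of the Investigator". Ponatinib is held around the radiation and may then resume, so a participant with stable disease can be irradiated and go on being assessed for response.

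**Both permitted sites can hold target lesions.** Section 9.1.2 classes bone lesions in general as non-measurable. It makes an exception for lytic or mixed bone lesions with an identifiable soft-tissue component "that can be evaluated by cross sectional imaging techniques such as CT or MRI can be considered target lesions if the" soft-tissue part is itself measurable. For the brain, exclusion 3.2.2 adds: "For asymptomatic brain metastases, appropriate clinical treatment may include observation with serial imaging". An untreated brain metastasis can therefore be present at entry, and nothing in Section 9 bars it from being a target.

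**Radiation rules for lesions.** Section 9.1.2 makes an already irradiated lesion non-measurable "unless there is objective evidence of progression of the lesion prior to study enrollment". Criterion 3.1.5 is to the same effect. The target-lesion text repeats the point for earlier radiation and extends it to other local treatment, saying that such "areas subject to other loco-regional therapy are usually not considered measurable unless there has been demonstrated progression of that lesion".

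**Scoring.** Section 5.1 item 18 fixes the targets at study start and has them followed for as long as treatment lasts. Section 9.1.3 defines partial response as "At least a 30% decrease in the sum of the diameters of target lesions, taking as reference the baseline sum diameters". Best overall response stays open until progression (Section 9.1.3), and Section 1.4 counts a response at any time after treatment starts. Section 13.1 calls the drug promising if at least 4 of 20 participants respond.

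**The concern.** Participants with stable disease are non-responders at the moment they become eligible for radiation, and their response window is still open. If the irradiated lesion is a target and it shrinks, the plan has no rule that removes it from the sum, scores the time point as unknown, or stops later responses from counting. On the default reading, the effect of local radiation is credited to ponatinib.

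The existing safeguards do not separate the two effects. Confirmation at 4 weeks or more shows that the shrinkage lasts, not what caused it. Central review (Section 9.1.6) has no rule to apply, and the scan package from outside sites is reports and images, with no radiation record required. The ORR error runs in the drug's favour, there is no control arm to offset it, and the primary conclusion turns on very few responders.

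**Working it through.** **1. Reproduce the plan's figures (Section 13.1).** Inputs: n = 20, pass if X ≥ 4, null ORR 10%, alternative 30%.

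P(X ≥ 4) = 1 − Σ C(20,x) pˣ (1−p)²⁰⁻ˣ for x = 0 to 3.

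- p = 0.10: 1 − (0.12158 + 0.27017 + 0.28518 + 0.19012) = 0.1330. The plan says 13%.
- p = 0.30: 0.8929. The plan says 89%.

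Both agree.

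**2. Does any existing text decide the case?**

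- Criterion 3.1.5 and the measurable-disease note in Section 9.1.2 decide whether a lesion irradiated *before* entry may be used. They do not address radiation given later.
- The sentence on loco-regional therapy in the target-lesion text has no time limit. It sits among the rules for selecting targets, is qualified by the word usually, and gives no scoring instruction for a lesion that is already a target.
- The unknown category in Section 9.1.3 is for insufficient or unevaluable data. An irradiated lesion can still be measured, so the category does not clearly apply.

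The case is left open, and the default is to keep measuring the lesion.

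**3. How large must the irradiated lesion be?** Let s be its share of the baseline sum and f its proportional shrinkage. If the other targets do not change, the sum falls by s × f. Partial response needs s × f ≥ 0.30, so s ≥ 0.30 / f.

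| Shrinkage f | Share needed, others unchanged | Share needed, others down 10%: (0.30 − 0.10)/(f − 0.10) |
|---|---|---|
| 50% | 60% | 50% |
| 75% | 40% | 31% |
| 100% | 30% | 22% |

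Hypothetical example: a 40 mm bone soft-tissue lesion and a 30 mm lung lesion give a baseline sum of 70 mm. If radiation takes the bone lesion to 15 mm and the lung lesion does not change, the sum is 45 mm. The fall is 25/70 = 35.7%, which meets the partial response criterion.

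**4. Effect of exactly one false responder.** One of the 20 participants is scored a responder because of radiation. At a true ORR of 10%, the trial passes if at least 3 of the other 19 respond:

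P(X ≥ 3; 19, 0.10) = 1 − (0.13509 + 0.28518 + 0.28518) = 0.2946, or 29.5%.

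**5. Effect of an assumed conversion rate.** Let q be the chance that a true non-responder is scored a responder because of radiation. The apparent ORR is 0.10 + 0.90q. The documents give no q, so these values are assumptions.

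| q | Apparent ORR | P(X ≥ 4 of 20) | Expected false responders (18 × q) |
|---|---|---|---|
| 0 | 10.0% | 13.3% | 0 |
| 1% | 10.9% | 16.7% | 0.18 |
| 2% | 11.8% | 20.4% | 0.36 |
| 5% | 14.5% | 32.8% | 0.90 |

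**The case against.** The strongest reply has four parts.

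- **Section 9 does not tell anyone to keep an irradiated target in the sum.** This is correct. A reader might infer such a rule from the way targets are fixed and followed, but none is written. The loco-regional sentence could even be read the opposite way. What stands is that the text is silent or ambiguous and retention is only the default. Two readers could score the same participant differently, and the choice could be made after the result is seen.
- **The route is narrow.** This is also correct. Most bone metastases are non-measurable and cannot move the target sum. Brain lesions irradiated before entry are generally not measurable. A lesion that has grown enough to meet progression before radiation closes the response window. The lesion must also dominate the sum, and the response must be confirmed. All of this limits how often the problem arises but does not settle the scoring when it does.
- **The size may be overstated.** A reader might infer that the type I error simply goes from 13% to 32%, using P(X ≥ 3 of 20) = 32.3%. The documents do not support that. It adds a certain false responder to 20 other participants, and with one false responder *among* the 20 the figure is 29.5%. That figure is itself conditional on the event happening. The 5% row implies nearly one false responder per trial, which is hard to square with so narrow a route.
- **Radiation would not go wholly unrecorded.** Outside sites send source documents to the Coordinating Center, which verifies response (Appendix D, Sections 2.2, 2.4 and 5.1), and missed doses go on the eCRF (Section 6.3). A reader should therefore not infer that no trace exists. But none of these steps requires the central reviewers to be told which lesion was irradiated and when, or tells them what to do about it.

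**Conclusion.** The concern holds in limited form. The plan permits radiation to two sites that can hold target lesions, in participants who are not yet responders, and does not say how such a lesion is then scored. On the default reading, radiation shrinkage can produce a response in the primary endpoint.

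The likely frequency is low and cannot be estimated from the documents. The consequence of a single case is large because the threshold is 4 of 20: at a true ORR of 10%, the chance of declaring promise is 29.5% given exactly one false responder, against 13.3% with none. Assumed conversion rates of 1% to 5% give 16.7% to 32.8%. These figures assume independent participants and 20 analysed.

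The documents do not show that the stated 13% and 89% are wrong. Both stand if no irradiated lesion can create a response, and the sample size need not change. The rule should be fixed in advance because it is cheap and otherwise leaves room for judgement after the fact.

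**What to change.** Add to Sections 9.1.2 and 9.1.3:

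- A partial or complete response first documented after radiation to a target lesion does not count toward ORR, unless the non-irradiated target lesions alone show a fall of at least 30% from their own baseline sum with no progression elsewhere.
- Progression in an irradiated lesion still counts as progressive disease.
- For such lesions, this rule overrides two parts of Section 9.1.3: the note that makes the overall assessment unknown when target data are missing, and the use of the full baseline sum as reference. Without this statement the new rule would conflict with the existing text.

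Record the site and dates of on-study radiation on the eCRF and send them to the central reviewers with the scans. Report a sensitivity ORR that excludes every response first documented after radiation.

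The cost is a few lines of text, one eCRF field and one extra tabulation, with no added scans or readers. The downside is that a few irradiated participants may not be scorable as responders later, including some in whom the drug did work. When radiation may be given is unchanged.

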### **6.13 Prohibited Treatment**

The following concurrent medications and treatments are prohibited:

- Any other anti-cancer therapy including, but not limited to, chemotherapeutic agents, immunotherapy, biological response modifiers, surgery and/or systemic hormonal therapy (hematopoietic growth factors are permitted).
- Use of any other investigational drug or device.
- Use of medications that are known to be associated with the development of Torsades de Pointes (see [Appendix B](#)).
- Herbal preparations or related over-the-counter preparations containing herbal ingredients either during or within 2 weeks prior to the first dose of ponatinib.
- Elective surgery requiring in-patient care.

